8.6.2 Data collected

Questionnaire

- For Wave 2 only: whether HCP took part in Wave 1
- Gender
- Country of practice

- Year of qualification (as a doctor, as a specialist neurologist)
- Work setting (public/private; university/community hospital)
- Prescribed at least one dose of Aubagio
- Behaviour and knowledge relating to Aubagio risk management.

8.6.3 Site / Physician questionnaire

Not applicable.

8.6.4 Screening log (if applicable)

Not applicable.

8.6.5 Patient data

Not applicable

8.6.6 Procedure for withdrawal of patients from study follow-up schedule

Not applicable.

8.6.7 Logistic aspects

Not applicable.

8.7 DATA ANALYSIS

8.7.1 Primary analysis

Descriptive analyses only (e.g. frequency distributions for each item) will be performed on the overall population of participating prescribers.

The response on knowledge is considered satisfactory if participants provide >70% correct answers. There is no pre-defined threshold for the behavior.

8.7.2 Secondary analysis

- 1. The analysis will be descriptive. Knowledge and behavior are analysed in conjunction with each other. Where it is found to be <70%, more in-depth analysis will be considered (e.g. to identify specific areas where knowledge is low).
- 2. Responses in sub-groups compared to the rest of the sample. Sub-groups to be analysed are:
 - Number of patients HCPs treat with Aubagio
 - Length of time since last prescription
 - University/community, public/private hospital
 - General neurologist or MS specialist
 - Country

8.7.3 Interim analysis

No interim analysis is planned for this registry. A report per wave is planned.

8.8 **QUALITY CONTROL**

8.8.1 Data collection, validation and data quality control at MAH/MAH representative level

Data will be collected electronically directly from HCPs using a secure system.

Data will be anonymised and stored on a password protected computer in a locked office. The data will be stored electronically in this way for 5 years (from completion of Wave 2) and then erased.

Analysis will be undertaken using the IBM statistical software package by qualified research personnel employed by Ipsos.

All data will be self-reported, and there will be no opportunity to verify source data.

8.8.2 Data quality control at site level

Not applicable.

8.9 LIMITATIONS OF THE RESEARCH METHODS

All data supplied will be self-report, and it will not be possible to objectively verify information (e.g. work setting).

The study uses descriptive statistics only. Therefore it is not possible to determine whether findings are statistically significant or could be due to chance. However, given that the main objective is to measure knowledge, descriptive statistics are sufficient

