The survey will be conducted in two waves at 18 months and at 3 years after launch of Aubagio in at least 5 countries, including at least 2 of the most populated 5 European Union (EU) countries. The surveys will be conducted online, using a structured questionnaire. Results will be analysed and reported to the EMA.

Population

The population for this study will be a sample of HCPs involved in the treatment of MS using Aubagio. To have wide coverage of HCPs across the EU, the survey will be conducted in at least 5 countries of the EU. Based on an estimation of Aubagio prescribers across Europe, the survey will be administered to approximately 200 HCPs.

Variables

The following elements will be collected and assessed at each wave:

- Knowledge of the HCP Education/Discussion guide
- 2. Use of HCP Education/Discussion guide, and suggestions for change of the guide
- 3. Knowledge of the key points of the content:
 - a. Hepatic effects and associated assessment of liver enzymes
 - b. Pregnancy and lactation. It includes pregnancy check, contraception information and implementation, and knowledge on the accelerated elimination procedure of teriflunomide from the blood, and existence of the Pregnancy Registry.
 - c. Hematological effects
 - d. Infections
- 4. Behaviour relating to liver enzyme monitoring and discussion of risks with patients (including delivery of Patient Card (PC) to patients).

Data sources

Data regarding the known distribution of neurologists and MS sub-specialists for participating countries will be supplied by the MAH. All other data will be collected via HCP self-report in a questionnaire.

Study size

The survey will be administered to 200 HCPs.

Data analysis

Descriptive analyses only will be performed. Sub-populations will be analyzed to identify patient groups that may require further education efforts. A threshold of 70% will be defined as 'adequate' knowledge. There is no pre-defined threshold for behavior.

Milestones

The survey will be conducted in 2 waves at 18 months and at 3 years after launch of Aubagio in at least 5 countries, including launch in at least 2 of the most populated 5 EU countries.

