8.5 STUDY SIZE

8.5.1 Determination of sample size

Based on an estimation of Aubagio prescribers across Europe, the survey will be administered to approximately 200 HCPs.

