8.5.2. Sample size

It is planned to recruit 200 HCPs.

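### Section 8.9 wrongly says a descriptive study cannot assess chance; results judged against 70%, and sub-group differences, should carry 95% confidence intervals

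*Protocol*

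**What the plan says.** The Synopsis sets the criterion: "A threshold of 70% will be defined as 'adequate' knowledge". Section 8.7.1 puts it as "The response on knowledge is considered satisfactory if participants provide >70% correct answers", and describes the analysis as "Descriptive analyses only (e.g. frequency distributions for each item) will be performed on the overall population of participating prescribers". Section 8.7.2 attaches a consequence to a low result: "Where it is found to be <70%, more in-depth analysis will be considered". It also plans "Responses in sub-groups compared to the rest of the sample" for five factors: number of patients treated, time since last prescription, hospital type, general neurologist or MS specialist, and country. The Synopsis gives the purpose of the sub-group work as finding groups that may need more education. It calls them patient groups, although the respondents are HCPs.

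Section 8.5.1 explains the sample size in one sentence: "Based on an estimation of Aubagio prescribers across Europe, the survey will be administered to approximately 200 HCPs". Section 8.5.2 adds "It is planned to recruit 200 HCPs". Neither says whether this is per wave or over both waves, and no precision target is given.

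Section 8.9 notes that only descriptive statistics are used and continues: "Therefore it is not possible to determine whether findings are statistically significant or could be due to chance". It adds that descriptive statistics suffice because the main aim is to measure knowledge.

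**The concern.** The step in 8.9 from descriptive to unable to assess chance is wrong. Leaving out hypothesis tests does mean that no significance statement will be made. It does not prevent anyone from showing how far a percentage could have moved by sampling alone, which is what a confidence interval does. The supporting argument points the other way too: measuring a population's knowledge from a sample is the setting in which precision should be stated.

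The error has consequences because the plan sets its estimates against a benchmark and against each other, and reports them to the EMA. With point estimates alone, an observed 72% and an observed 68% fall on opposite sides of the criterion although both are compatible with a true 70%. Country and other sub-group differences are noisier still, because the groups are small.

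**Working it through.** **Inputs.** From the protocol: 200 HCPs (8.5.1, 8.5.2), a 70% criterion (Synopsis, 8.7.1, 8.7.2), at least five countries (8.2.4.1), sub-group against rest (8.7.2). Assumed: the 70% is a share of HCPs correct on a yes/no item; 200 is per wave; five equal countries of 40; simple random sampling; two-sided 95% level.

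**The plan's own figure.** The 200 cannot be reproduced. It rests on an estimated number of prescribers that is not given, with no precision or power target.

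**1. Half-width for one proportion at 70%:** 1.96 × √(0.70 × 0.30 / n)
- n = 200: 1.96 × √(0.21/200) = 6.4 points
- n = 100 (if the 200 covers both waves equally): 1.96 × √(0.21/100) = 9.0 points
- n = 40 (one country): 1.96 × √(0.21/40) = 14.2 points

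Wilson intervals at an observed 70% are 63.3% to 75.9% for n = 200 and 54.6% to 81.9% for n = 40.

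**2. Results compatible with 70% at n = 200.** The Wilson interval excludes 70% only at 153/200 (76.5%) or more, or at 127/200 (63.5%) or fewer. Observed results from 128/200 (64%) to 152/200 (76%) therefore have intervals that include 70%.

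**3. Chance of landing on the wrong side of 70%** (exact binomial):

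| True share | n = 200 | n = 40 |
|---|---|---|
| 60%, observed above 70% | 0.1% | 7.1% |
| 65%, observed above 70% | 5.8% | 20.5% |
| 68%, observed above 70% | 24.9% | 33.6% |
| 72%, observed below 70% | 23.8% | 31.6% |
| 75%, observed below 70% | 4.5% | 17.9% |
| 80%, observed below 70% | under 0.1% | 4.3% |

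For the whole sample the risk is confined to true values within about 6 points of 70%. In a group of 40 it reaches further.

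**4. Sub-group against rest, 70% in both:** standard error √(0.21 × (1/40 + 1/160)) = 8.1 points, so the half-width is 1.96 × 8.1 = 15.9 points. With no true difference, a gap of 10 points or more arises in about 22% of samples (z = 10/8.1 = 1.23).

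**5. Sensitivity to the assumptions.**
- Mean score instead of a share correct: with an assumed between-HCP standard deviation of 10 to 20 points, the half-width at n = 200 is 1.96 × SD/√200 = 1.4 to 2.8 points. For 40 against 160 it is 1.96 × SD × √(1/40 + 1/160) = 3.5 to 6.9 points.
- Finite population: multiplying the variance by (N − 200)/(N − 1) reduces the 6.4 points to 4.9 if there are 500 prescribers and to 6.2 if there are 5,000 (both assumed).

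**The case against.** The best reply is that the protocol never excludes confidence intervals. Frequency distributions are given in 8.7.1 only as an example, and the choice of interval is commonly left to a statistical analysis plan. That stands as far as it goes: a reader might infer that intervals will not be reported, and the protocol does not say so. But 8.9 takes a position on the point. It says chance cannot be assessed and that this is acceptable, and that statement is wrong wherever the detail is later filled in.

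Several stronger readings are tempting and should not be made.
- *That sampling noise will be mistaken for adequate or inadequate knowledge.* At n = 200 this can happen only near 70%, and 8.9 does warn that findings could be chance. The stated consequence of a low result is mild: deeper analysis is to be considered.
- *That a sub-group gap of a given size would set off re-education.* The Synopsis speaks of groups that may need more education, but no rule ties an action to a gap.
- *That the interval for the change between waves is at issue.* The plan contains no such comparison; 8.7.3 plans one report per wave.

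Two technical objections also stand. The wording in 8.7.1 can mean a score per participant. If the result were then the share of participants who pass, no benchmark for that share is stated and the wrong-side probabilities above would not apply; if it were a mean score, intervals would probably be narrower. And recruitment by panels, telephone and snowballing (8.2.4.1) is not probability sampling, so an interval describes sampling variation only and does not address selection bias. Section 8.9 does not offer this as its reason, but any replacement text should say it. Finally, intervals for five sub-group factors over many items could be read as tests, so they need a label.

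**Conclusion.** The point holds in a limited form. The inference in 8.9 is incorrect, and it bears on results that the plan sets against 70% and on sub-groups that it compares with the rest. On the share-correct reading, with random sampling assumed, the uncertainty is about 6.4 points at n = 200 (9.0 if the 200 spans both waves), about 14 points for a country of 40, and about 16 points for that country against the other 160. The country figures also assume an equal split over five countries. Under a mean-score reading the sizes change, probably downwards, but the need to show precision does not. The survey remains usable. A clear result well away from 70% in the whole sample is not in doubt; results near 70%, and most country-level contrasts, need an interval to be read properly.

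**What to change.** In 8.7.1 and 8.7.2, state that each knowledge result judged against 70% is reported with a 95% confidence interval (Wilson for a proportion), and that each sub-group-versus-rest difference is also given with one. Keep the 70% criterion as it is, show the interval beside it, and say when the interval includes 70%. Label the sub-group intervals as descriptive and unadjusted for multiplicity.

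In 8.9, replace the sentence rather than delete it. Suggested text: *No hypothesis tests are planned. Sampling uncertainty is shown by 95% confidence intervals, which do not cover selection bias from non-probability recruitment (panels, telephone, snowballing).*

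This needs no more respondents, questions or tests; the intervals come from data already planned. The downside is that some results will read as inconclusive: at n = 200, on the share-correct reading, those observed from 64% to 76%.

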8.10 OTHER ASPECTS

Not applicable

9 PROTECTION OF HUMAN SUBJECTS

9.1 RESPONSIBILITIES OF THE PHYSICIAN/HEALTH CARE PROVIDERS

Not applicable.

9.2 ETHICAL, REGULATORY AND ADMINISTRATIVE RULES

9.2.1 Ethical principles

This study will be conducted in accordance with the principles laid by the 18th World Medical Assembly (Helsinki, 1964) and all subsequent amendments.

9.2.2 Laws and regulations

Each participating affiliate should locally ensure all necessary regulatory submissions (e.g.: IRB/IEC) are performed in accordance with local regulations including local data protection regulations.

9.2.3 Data protection

The participant's personal data which may be included in the MAH/MAH REPRESENTATIVE database shall be treated in compliance with all local applicable laws and regulations.

The web services provided as educational material and alongside the educational material will be completely separate from any promotional activities. Personal information provided by HCPs as part of this survey will not be used for any promotional activities.

When archiving or processing personal data pertaining to the participants, the MAH/MAH REPRESENTATIVE shall take all appropriate measures to safeguard and prevent access to this data by any unauthorized third party.

9.2.4 Insurance

Not applicable. This is a survey using a mandatory template, not a treatment study.

9.2.5 Secrecy agreement

Not applicable.

9.2.6 Record retention

Ipsos shall arrange for the retention of study documentation until the end of the study. In addition, Ipsos will comply with specific local regulations/ recommendations with regards to patient record retention.

It is recommended that Ipsos retains the study documents at least five years (5) after the completion or discontinuation of the study.

However, applicable regulatory requirements should be taken into account in the event that a longer period is required.

9.2.7 Discontinuation of the study

The MAH/MAH representative can decide at any time and for any reason to discontinue the study.

If appropriate, according to local regulations, Ethic Committee(s) (IRB/IEC) and Competent Authorities should be informed.

9.2.10 MAH/MAH representative audits and inspections by competent authorities

Ipsos agrees to allow the MAH/MAH representative auditors/Competent Authorities inspectors to have direct access to his/her study records for review, being understood that this personnel is bound by professional secrecy, and as such will not disclose any personal identity or personal medical information. Access to the source document will not be allowed (because no informed consent form is signed)

Ipsos will make every effort to help with the performance of the audits and inspections, giving access to all necessary facilities, data, and documents.

The confidentiality of the data verified and the protection of the patients should be respected during these inspections.

Any result and information arising from the inspections by the competent authorities will be communicated by Ipsos to the MAH/MAH representative.

Ipsos shall take appropriate measures required by the MAH/MAH representative to take corrective actions for all problems found during the audit or inspections.

10 MANAGEMENT AND REPORTING OF ADVERSE EVENTS/ADVERSE REACTIONS

Not applicable – this is a survey and will not generate AEs.

11 PLANS FOR DISSEMINATING AND COMMUNICATING STUDY RESULTS

11.1 OWNERSHIP AND USE OF DATA AND STUDY RESULTS

No use of the data will be possible without the authorisation of the MAH/MAH REPRESENTATIVE conducting the study.

11.2 PUBLICATIONS

There are no plans to publish the data from this survey.

13 APPENDICES

Appendix 1 List of stand-alone documents

Documents listed in Appendix 1 can be maintained separately from the study protocol. They should be clearly identifiable and provided on request.

Number	Document reference number	Date	Title
1	GZEMEA.AUBA.15.09.0544	21 January 2016	Aubagio RMP Materials Study
2	4_130408 EU HCP Education Guide final	8 th April 2013	HCP education guide (as submitted to CHMP)
